1 PROTOCOL SUMMARY

1.1 SYNOPSIS

Title:	Increasing African Immigrants' Breast Cancer Screening
Grant Number:	R21MN012863
Study Description:	The barriers and facilitators to breast cancer screening for other minority groups from underserved populations, such as African Americans and Latina women have been studied. Less is known about these for African immigrant women and how to most effectively engage their participation in regular screening. The long term goal of the proposed project is to conduct a clinical trial that tests the feasibility of an adapted intervention to increase breast cancer screening rates for African-born immigrants. The study team plans to pursue the following specific aims: (1) Identify barriers and facilitators to breast cancer screening among African-born immigrants and (2) Culturally adapt and pilot test the Witness Project breast cancer education program for African-born women.
Objectives * :	Primary Objective: Adapt and pilot the Witness Project breast cancer education program. Secondary Objectives: Identify barriers and facilitators of breast cancer screening
Endpoints * :	Primary Endpoint: change from baseline assessment of mammogram screening intention and mammogram location and appointment. Secondary Endpoints: change from baseline assessment of perceived breast cancer risk and self-efficacy for mammography.
Study Population:	Men or women 18 and older; stakeholder or leader in African immigrant community; English or French speaking (Aim 1) African-born women 40 years and older; English or French speaking (Aim 1) African-born women 38 years and older; English or French speaking (Aim 2)
Phase * or Stage:	Not Applicable
Description of Sites/Facilities	Participants will be enrolled at one site (Icahn School of Medicine at Mount Sinai) in collaboration with African immigrant-serving community organizations.
Enrolling Participants:	
Description of Study	

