3 OBJECTIVES AND ENDPOINTS

OBJECTIVES	ENDPOINTS	JUSTIFICATION FOR ENDPOINTS
Primary		
Adapt and pilot the Witness Project breast cancer education program	
Primary Outcome Measure:
 
1. Mammogram intention: Participants' intentions to complete breast cancer screening by responding to:
 
A. For women who had a mammogram in the past: Do you think you will have another one? Yes, later this year (2023) Yes, next year (2024) Yes, in two years (2025) No Not sure/don't know
 
B. For women who never had a mammogram in the past: Do you think you will have one? Yes, later this year (2023) Yes, next year (2024) Yes, in two years (2025) No Not sure/don't know
 
2. Mammogram location and appointment: Do you know where you could go to get a mammogram? Yes No Not sure
 
Secondary Outcome Measures:
 
3. Perceived Risk: Participants' perceived risk of developing breast cancer: What do you think are the chances that you will have breast cancer at some point in your life? (1. Very low 2. Somewhat low 3. Moderate
	
Intention to screen is hypothesized to be a dependent variable.
 
Perceived risk is hypothesized to be mediator variable that could explain the causal mechanisms of the intervention.

OBJECTIVES	ENDPOINTS	JUSTIFICATION FOR ENDPOINTS
	
4. Somewhat high 5. Very high) [Time Frame: Immediate]
 
4. Comparison Perceived Risk: Participants' perceived risk of developing breast cancer: Compared to the average person your age and gender, would you say that you are (1. Less likely to get breast cancer 2. About as likely to get breast cancer 3. More likely) to get breast cancer [Time Frame: Immediate]
 
5. Self-Efficacy for Mammography: Ten items will be used to examine participants' self-efficacy for undergoing mammography using a 5-point Likert-type scale. (Full scale from 1 to 5, with higher score indicating greater self-efficacy) [Time Frame: Immediate]
	Self efficacy is hypothesized to be a mediator variable that could explain the causal mechanisms of the intervention.
Secondary		
Identify barriers and facilitators of breast cancer screening	N/A - survey/interview completion	N/A
Tertiary/Exploratory		
N/A	N/A	N/A

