4 STUDY DESIGN

4.1 OVERALL DESIGN

The goal of Aim 1 is to collect formative data via a mixed methods approach and use those results to culturally adapt the Witness Project for African immigrant populations. Cultural adaptation will follow the stage model outlined by Barrera et al.⁴⁸ The model includes five stages: 1) information gathering to determine which intervention components to modify; 2) preliminary adaptation design that integrates information from stage 1 to inform preliminary modification of the original intervention; 3) preliminary adaptation tests to pilot the intervention for feasibility and acceptability, 4) adaptation refinement with decisions informed a leadership team/advisory board; and 5) cultural adaptation trial to test the effectiveness of the intervention in changing health outcomes. As this is the first step in this line of research, the proposed study will only follow stages 1-4.

The Witness Project has three main components that will be culturally adapted: 1) educational presentation addressing myths, barriers and values related to breast cancer and mammography, 2) culturally matched, peer led narrative about breast cancer experience, 3) experiential education about breast anatomy and self-examination.

Based on "NIH Protocol Template for Behavioral and Social Sciences Research"

11

The “point of interface” (i.e., merging quantitative and qualitative data) will be associations between mammography screening and HBM constructs (e.g., perceived risk, self-efficacy) and any socio-demographic characteristics (i.e., preferred language, health literacy level). The quantitative results will inform the refinement of the qualitative questions. For example, if an association is found between self-efficacy and screening, we will ask in-depth questions about self-efficacy and suggestions for how it could be improved in this population.

The design chosen for the pilot-test is a one-group pretest –posttest. All of the enrolled participants will receive the same intervention in their preferred language (English or French). To measure the impact of the intervention, will conduct a pre-post assessment of key variables around perceived risk for breast cancer, the intention to complete a mammogram, and self-efficacy related to seeking and completing breast cancer screening. This trial will also assess the feasibility and acceptability of the intervention.

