session and f) completion of the post-program survey including feasibility questionnaire and feedback discussion. After the completion of the question and answer session, participants will be given breast cancer resource guides with local information about how and where to obtain screening. The program will take approximately 90 minutes to complete. Participants will receive an incentive (\$60 gift card) for their participation. Participants will complete a pre-program survey and a post-program survey to assess changes in HBM constructs. The post-program survey will also include a feasibility questionnaire.^{62,63,64,65} The programs will be evaluated using a program summary template that [name] and colleagues have used in previous studies. The summary collects information about the length of the program, number of participants attending the program, gender of program participants, location and site of the program, number of staff and volunteers present, and type of site (faith-based or community-based).

For both in person and virtual educational programs, demographic and pre-post surveys will be primarily collected via RedCap. For virtual programs, participants will be provided with RedCap survey links via chat. For in person programs, participants will be able to complete surveys through RedCap on their own devices or on devices provided by the study team. Hard copies of the surveys will also be available for completion for in person educational programs. All pre and post assessments, collected via RedCap or hard copy of surveys, will be linked only via participant study ID. Assessments will not collect any PHI. They will be anonymous as participant names will not be collected.

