9 STATISTICAL CONSIDERATIONS

9.1 STATISTICAL HYPOTHESES

Descriptive statistics will provide summary information about the feasibility of recruitment, acceptability and cultural sensitivity of the program and satisfaction with the program. An arbitrary cutoff value of 80% acceptance will determine the interventions' feasibility for the study. Some parameters include the proportion of eligible participants who are contacted, enrolled, agree, and disagree with the acceptability and cultural sensitivity of the program. Thus, if at least 80% of the participants exceed the previous parameters, the developed program will be determined to be feasible.

- Primary Endpoints:

We hypothesize that we will observe a change in the assessment of mammogram screening intention and knowledge of places where it is possible to obtain a mammogram appointment in the participants who will take part in the pilot test of the culturally adapted intervention (posttest), compared to baseline (pretest).

- Secondary Endpoints:

We hypothesize that we will observe a change in assessment of perceived breast cancer risk and self-efficacy for mammography in the participants who will take part in the pilot test of the culturally adapted intervention (posttest), compared to baseline (pretest).

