9.4 STATISTICAL ANALYSES

9.4.1 GENERAL APPROACH

For Aim 1 demographic characteristics of the participants will be reported. Data from the quantitative surveys will be analyzed to identify predictors of non-adherence to breast cancer screening. We will conduct univariate and bivariate analyses of the data to provide descriptive summaries of the data, including demographics and responses to primary outcome measures. Data from the audio-recorded in-depth interviews will be transcribed verbatim from audio recordings (using a transcription service). Analyses of the qualitative data will be conducted using the PEN-3 model, which is a method of analyzing data focusing on social processes and actions. The goal of our qualitative research is to identify the unique barriers and facilitators African immigrant women encounter with breast cancer screening. In line with this approach, the coding steps of open coding, axial coding, and selective coding will be used to identify categories and develop properties. Memoing will be conducted throughout the process. A constant comparative method will be used to generate theoretical categories and refine concepts.

For Aim 2, we will conduct univariate and bivariate analyses of the data to provide descriptive summaries of the data, including demographics and responses to primary outcome measures. Independent samples t tests will be used to compare changes in the primary outcomes measures pre-education and post-education. Using a pre-post test design, we will analyze differences in the three primary outcomes: screening intentions, self-efficacy and perceived risk immediately before viewing the educational program and immediately after viewing the program.

To determine program efficacy and sample size estimates for a future intervention, a generalized linear modelling approach will be used with logistic regression. We will use a repeated measures ANOVA to analyze differences in the primary outcomes: screening intentions and HBM constructs (e.g., self-efficacy and perceived risk) immediately before viewing the educational program and immediately after viewing the program. We will conduct univariate and bivariate analyses of the data to provide descriptive summaries of the data, including demographics and responses to primary outcome measures.

Based on "NIH Protocol Template for Behavioral and Social Sciences Research"

23

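### The Aim 2 analysis does not follow the plan's own primary endpoints and applies independent samples t tests to linked pre-post data

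*Combined protocol and SAP*

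**What the plan says.** **Endpoints.** The synopsis (Section 1.1) gives "Primary Endpoint: change from baseline assessment of mammogram screening intention and mammogram location and appointment". Section 3 lists the same two as primary. The location item is "Do you know where you could go to get a mammogram", answered Yes, No or Not sure. Perceived risk (absolute and comparative) and self-efficacy are secondary. Section 9.1 keeps this split and hypothesises a "change in the assessment of mammogram screening intention and knowledge of places where it is possible to obtain a mammogram appointment".

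**Outcomes analysed.** Section 9.4.1 states "we will analyze differences in the three primary outcomes: screening intentions, self-efficacy and perceived risk". Section 9.3 calls intention and the Health Belief Model constructs primary. Section 9.4.2 gives a third list: screening status and those constructs. Section 4.1 says the team "will conduct a pre-post assessment of key variables around perceived risk for breast cancer, the intention to complete a mammogram, and self-efficacy" and leaves out location.

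**Tests.** For the pre-post comparison, Section 9.4.1 names independent samples t tests and also a repeated measures ANOVA. It adds a logistic regression without an outcome. The ANOVA and the logistic regression are tied to program efficacy and future sample size. Section 4.1 describes a one-group pretest-posttest design, and Section 6.1.1 says "All pre and post assessments, collected via RedCap or hard copy of surveys, will be linked only via participant study ID".

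**Intention.** The options in Section 3 are "Yes, later this year (2023) Yes, next year (2024) Yes, in two years (2025) No Not sure", the last also covering don't know. No numeric code or cut-point is given. The rationale in Section 10.4 speaks of intention within two years but does not place Not sure.

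**The concern.** Four things do not fit together.

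- A hypothesised primary endpoint, location knowledge, has no suitable pre-post test.
- Measures declared secondary could be reported as primary results.
- Two tests of the same change are planned, one of which ignores the pairing, and nothing says which governs.
- Intention cannot be averaged without an invented code, because No and Not sure have no agreed order. The effect carried into planning the next trial could then depend on that code.

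With no responder definition and two conflicting lists of primaries, both the cut-point and the headline outcome could be chosen after the data are seen.

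**Working it through.** **The plan's own figure.** Section 9.2 gives ±12% for 64 participants. 1.96 × √(0.5 × 0.5 / 64) = 0.1225, so it reproduces. It is the margin for a single proportion, not for a pre-post change.

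**Inputs.** From the documents: n = 64, one group, linked surveys, 95% confidence. Assumed, because the documents give none of them: complete pairs, two-sided 5% (no level is stated for Aim 2), switching rates, pre-post correlation r, and no allowance for group programs.

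**Location, one worked case (assumed counts).** Yes rises from 38 to 46 of 64, with 9 gains and 1 loss.
- Unpaired: z = 0.125 / √(2 × 0.65625 × 0.34375 / 64) = 1.49, p = 0.137.
- Exact McNemar: 2 × (10 + 1) / 2¹⁰ = 0.021.

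**Binary outcomes, power by simulation (40,000 runs per case).** Baseline Yes p₁ is 40%, 50%, 56% or 70%; a proportion b moves to Yes and c moves away, so p₂ = p₁ + b − c. Half-widths are:
- unpaired 1.96 × √{[p₁(1−p₁) + p₂(1−p₂)] / 64}
- paired 1.96 × √{[b + c − (b−c)²] / 64}

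The implied correlation is r = (p₁ − c − p₁p₂) / √[p₁(1−p₁)p₂(1−p₂)].

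| To Yes / away | Baseline | Implied r | Independent t | Exact McNemar | Half-width, unpaired / paired (points) |
|---|---|---|---|---|---|
| 20% / 3% | 40–70% | 0.59–0.40 | 45–70% | 80% | 17–14 / 11 |
| 15% / 3% | 40–70% | 0.66–0.55 | 14–29% | 54% | 17–15 / 10 |
| 25% / 8% | 40–56% | 0.38–0.32 | about 45–54% | about 60% | 17–16 / 13 |
| 25% / 8% | 70% | 0.07 | 66% | 60% | 14 / 13 |
| 27% / 10% | 40–56% | 0.30–0.23 | about 46–54% | about 54% | 17–16 / 14 |
| 27% / 10% | 70% | −0.06 | 65% | 54% | 14 / 14 |

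Example for the first row: paired, 1.96 × √[(0.23 − 0.17²) / 64] = 0.110; unpaired at 40%, 1.96 × √[(0.24 + 0.2451) / 64] = 0.171. With no net change (10% each way), actual error is 0.2–0.5% for the t test and 2.3–2.6% for McNemar.

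**A continuous scale such as self-efficacy.** The independent t test overstates the standard error by 1/√(1−r): 1.20 at r = 0.3 and 1.41 at r = 0.5. Its actual error, 2[1 − Φ(1.96/√(1−r))], is 0.019 and 0.006. For a change of 0.4 SD:

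| | r = 0.3 | r = 0.5 |
|---|---|---|
| Independent t, power | 64% | 66% |
| Paired t, power | 76% | 88% |
| Half-width, unpaired (SD) | 0.35 | 0.35 |
| Half-width, paired (SD) | 0.30 | 0.25 |

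With two time points the repeated measures ANOVA is the paired t test (F = t²), so it is sound for this scale.

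**Intention coding (constructed data).** Baseline: 16 this year, 14 next year, 6 in two years, 8 No, 20 Not sure. Six women move from Not sure to next year and four from Not sure to No.
- Codes 1–5 in listed order: [6 × (2−5) + 4 × (4−5)] / 64 = −22/64 = −0.344; SD of change 0.895; ratio 0.384; p = 0.003.
- No and Not sure swapped: [6 × (2−4) + 4 × (5−4)] / 64 = −8/64 = −0.125; SD 0.655; ratio 0.191; p = 0.13.
- Per arm for a two-arm trial at 80% power (control arm unchanged, same SD of change), 2 × (1.960 + 0.842)² / ratio²: 107 or 431.
- Any Yes goes from 36 to 42 of 64 under either code; exact McNemar 2 × 0.5⁶ = 0.031.

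If instead eight women move from Not sure to next year and none to No, both codings give 0.375 and 112 per arm. Coding matters for some response patterns, not all.

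**The case against.** **Location may be covered.** Section 9.4.1 applies t tests to the primary outcome measures in general, and Section 3 puts location under that label. This is a fair reading, but it only gives a paired three-option item an independent samples t test, and the next sentence lists three primaries without it. Section 9.4.2 does not help: its outcome is screening status, and its closing sentence concerns Aim 1.

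**The t tests may compare language groups.** There are to be 32 English and 32 French speakers. But the text sets pre-education against post-education, and Section 9.4.6 rules out subgroup analyses.

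**The power gap depends on the scenario.** This stands. Cases with few women moving away imply correlations of 0.40–0.66. With more switching and the same 17-point net gain, the gain from pairing shrinks. At a 70% baseline, where correlation is near zero, the independent t test has more power than exact McNemar. McNemar is itself conservative, with actual error of 2.3–2.6% in the no-change cases.

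**The 107 against 431 is illustrative.** This also stands. It rests on one constructed table, and the long-term goal in Section 2.1 is a trial of screening rates, not of mean intention.

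**It is a pilot.** Section 4.1 stops before the effectiveness stage, the 80% cutoff decides feasibility, and a paired ANOVA is already planned. This limits the weight of the point. But Sections 9.3 and 9.4.1 make efficacy and future sample size stated products of these analyses, and ANOVA does not suit unscored intention or the location item.

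**Conclusion.** The concern holds. The conflict over which outcomes are primary, the independent t tests on linked data and the unscored intention item are all in the current text and need no assumption. The numerical cost does rest on assumptions. For binary outcomes the loss of power ranges from large (45–70% against 80%) to small, and it reverses when pre-post correlation is near zero. For a continuous scale at r = 0.3 to 0.5, power is 64–66% against 76–88%. The error is conservative: it widens intervals and does not raise the false-positive rate when correlation is positive. The larger risk is to interpretation: secondary scales reported as primary, and an intention effect that can depend on an unstated code. This should be fixed before analysis; it does not affect the feasibility decision.

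**What to change.** 1. Use the Section 3 hierarchy in Sections 4.1, 9.3 and 9.4: intention and location primary, perceived risk and self-efficacy secondary.
2. Delete the independent samples t tests.
3. Fix responder definitions in advance. One option is any dated Yes against No or Not sure for intention, and Yes against No or Not sure for location. Two years appears only in the amendment rationale, so state whether the 2025 option counts: from a 2023 survey it can fall beyond 24 months. If any surveys fall in 2024 (the document carries an effective date of 1/26/2024), also say how the option labelled 2023 is handled.
4. For both primaries, report the paired difference in proportions with a 95% interval as the main result, plus an exact McNemar test. Add the full pre-post shift table for intention.
5. Keep the repeated measures ANOVA (or paired t test) for self-efficacy. Use a named paired method for the two perceived risk items, for example the Wilcoxon signed-rank test. Report all of these as secondary.
6. State the logistic regression's outcome, cut-point and handling of pairing, or remove it.

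**Cost.** Changes to the analysis text only, with no new data or participants; whether the dated response labels still fit should be checked separately. Dichotomising loses timing detail, which the shift table keeps. A ceiling is possible because recently screened women are now eligible: at an assumed baseline of 56%, 80% or 90% Yes, only 28, 13 or 6 of 64 women can move to Yes. Exact McNemar needs at least 6 changers all in one direction (6 to 0 gives p = 0.031; 5 to 0 gives 0.0625). That, and its conservatism, is why the interval should lead.

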The long term goal of the proposed project is to conduct a randomized clinical trial that tests the adapted intervention to increase breast cancer screening rates for African-born immigrants. In the short term, we plan to pursue the following specific aims: (1) Identify barriers and facilitators to breast cancer screening among African-born immigrants and (2) Culturally adapt and pilot test the Witness Project breast cancer education program for African-born women. Thus, we will culturally adapt an effective, innovative intervention to address this significant health disparity in African-born immigrant communities. Once we have pilot tested the feasibility and acceptability of the intervention, we will apply for R01 funding.

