6 STUDY INTERVENTION(S) OR EXPERIMENTAL MANIPULATION(S)

6.1 STUDY INTERVENTION ADMINISTRATION

6.1.1 STUDY INTERVENTION DESCRIPTION

Aim 1 of the study is formative research for a cultural adaptation of the Witness Project. Aim 2 is a pilot test of the adapted program that will inform a larger trial to test the efficacy of the intervention.

The educational aspect of the program will be modeled after our current community based programs, as noted above, using narrative formats. The programs will disseminate relevant, up-to-date information for breast cancer to eligible African-born immigrant women. Trained staff will conduct the educational programs. Trained staff will enroll and collect data from English- and French- speaking African-born immigrants working with our consultants. Eligible individuals will be: 1) women who are 38 years or older; 2) born in Africa; 3) read and speak English and/or French; 4) smartphone or computer with Zoom for virtual program participants. Information and resources about breast cancer and existing primary care clinical services, including the mobile mammography van operated by our institution as well as external mobile mammography van programs, will be available to all participants. We will inform both insured and uninsured participants about the Cancer Services Program and local clinical service resources for those without primary care physicians (PCPs) as well as questions to guide them about asking clinicians about breast cancer screenings when they have medical appointments.

The educational intervention program will include: a) reviewing of the IRB Research Information Sheet, b) confirmation of eligibility for the study, c) completion of a brief demographic survey and pre-program survey, d) narrative presentation with topics addressing the benefits of early detection of breast cancer through screening; education about disparities in breast cancer; education about disparities in breast cancer screening among African immigrant women; and the unique barriers and facilitators to screening for African immigrant women identified in Aim 1 of this study, e) interactive discussion / question/answers

Based on "NIH Protocol Template for Behavioral and Social Sciences Research"

16

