9.3 POPULATIONS FOR ANALYSES

Per-Protocol Analysis Dataset

Based on "NIH Protocol Template for Behavioral and Social Sciences Research"

Descriptive statistics will provide summary information about the feasibility of recruitment, acceptability and cultural sensitivity of the program and satisfaction with the program. An arbitrary cutoff value of 80% acceptance will determine the interventions' feasibility for the study. Some parameters include the proportion of eligible participants who are enrolled, agree, and disagree with the acceptability and cultural relevance of the program. Thus, if at least 80% of the participants exceed the previous parameters, the adapted program will be determined to be feasible and acceptable. To determine program efficacy and sample size estimates for a future intervention, we will use a repeated measures ANOVA to analyze differences in the primary outcomes: screening intentions and HBM constructs (e.g., self-efficacy and perceived risk) immediately before viewing the educational program and immediately after viewing the program. We will conduct univariate and bivariate analyses of the data to provide descriptive summaries of the data, including demographics and responses to primary outcome measures.

We expect only minor amounts of missing data from the surveys and feasibility questionnaires. However, we will examine any patterns of missing data and if needed, consider using missing data imputation methods.

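### Sections 9.3 and 9.4.1 promise to determine program efficacy, which a one-group, same-session pre-post pilot cannot do and which the protocol elsewhere leaves to a larger trial

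*Combined protocol and SAP*

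**What the plan says.** Two sections state the same purpose, "To determine program efficacy and sample size estimates for a future intervention". Section 9.3 reads "To determine program efficacy and sample size estimates for a future intervention, we will use a repeated measures ANOVA" and applies that ANOVA to screening intentions and Health Belief Model constructs, surveyed just before and just after the program. Section 9.4.1, in its Aim 2 text, reads "To determine program efficacy and sample size estimates for a future intervention, a generalized linear modelling approach will be used with logistic regression". It names no dependent variable for the logistic regression and then repeats the ANOVA.

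On design, Section 4.1 says "The design chosen for the pilot-test is a one-group pretest –posttest", with every participant receiving the program. Section 6.3 marks randomization and blinding as not applicable. Section 6.1.1 places the pre-program survey, presentation, discussion and post-program survey in one session of about 90 minutes. Surveys are completed in REDCap or on paper, linked by study ID, with no names collected.

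On scope, Section 4.1 lists five stages of cultural adaptation. The third pilots the program for feasibility and acceptability, and the fifth is a trial of effectiveness on health outcomes. It then says that "the proposed study will only follow stages 1-4". Section 6.1.1 says "Aim 2 is a pilot test of the adapted program that will inform a larger trial to test the efficacy of the intervention". Section 2.1 gives the long-term goal as a "randomized clinical trial that tests the adapted intervention to increase breast cancer screening rates for African-born immigrants".

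Section 9.1 hypothesizes only that a change will be observed. Its 80% cutoff concerns feasibility and acceptability; no criterion for efficacy is given. Section 9.2 justifies 64 participants by a margin of error of 12 percentage points at 95% confidence.

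**The concern.** Efficacy is a comparison with what would have happened without the program. With one group, that counterfactual has to be assumed, and the assumption is that nothing else would move the answers between the two surveys. That is hard to defend here. The same women answer the same questions twice within one session, and the second time they have just heard a talk whose message is that screening is good. Being asked again, and wanting to give the welcome answer, can both move responses in the direction the study hopes for.

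The plan contains no control, delayed post-test or limitation statement to qualify the claim. If it is followed as written, a significant pre-post difference would be reported as efficacy and could be carried in that form into the R01 application that Section 2.1 foresees. The protocol would also be claiming in Section 9 what Sections 4.1 and 6.1.1 assign to a later study.

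**Working it through.** **1. The plan's own figure.** Inputs: n = 64 and 95% confidence (Section 9.2). For one proportion at p = 0.5, half-width = 1.96 × √(p(1 − p)/n) = 1.96 × √(0.25/64) = 1.96 × 0.0625 = 0.1225. This reproduces the stated 12%. It is the precision of a single proportion among independent women. It is neither the precision of a pre-post change nor the power for a program effect. The plan gives no effect size, SD or pre-post correlation, so there is no efficacy calculation to reproduce.

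**2. What the pre-post difference contains.** For any outcome:

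mean(post − pre) = program effect + repeat-testing effect + residual social-desirability effect.

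The pilot observes only the left-hand side. There are three unknowns and one equation. A comparison group taking both surveys without the program would supply a second equation, and a delayed post-test would at least show whether the change lasts. The plan has neither. Neither the ANOVA nor the logistic regression can recover the split, because the information is not in the data.

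**3. The passages side by side.**
- Sections 9.3 and 9.4.1: this analysis determines efficacy.
- Section 6.1.1: a larger trial, informed by this pilot, tests efficacy.
- Section 4.1: stages 1 to 4 only; the effectiveness trial is stage 5.

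The first statement cannot stand with the other two.

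**4. How often an inert program would look effective.** The documents give no figure for non-program shifts, so the sizes below are assumptions. With two time points, the repeated measures ANOVA is equivalent to a paired t test. Let the program effect be zero and the non-program shift be s SDs of the change score. With n = 64, the test statistic is noncentral t with 63 degrees of freedom and noncentrality s × √64 = 8s. At an assumed two-sided 5% level, with women treated as independent, the chance of a significant result is:

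| s (assumed) | noncentrality 8s | chance of significance |
|---|---|---|
| 0.1 | 0.8 | 12% |
| 0.2 | 1.6 | 35% |
| 0.3 | 2.4 | 66% |
| 0.5 | 4.0 | 98% |

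No significance level is stated for Aim 2; the 0.15 in Section 9.4.2 is given for Aim 1. A looser threshold would raise every row.

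**5. The sizing clause.** Section 6.1.1 expects the pilot to inform the larger trial, so supplying planning inputs is within scope. Recruitment, completion and baseline proportions are legitimate outputs of one group. A between-arm effect is not, for the reason in step 2. There is also a change of outcome: Section 3 measures intention, knowledge of where to go, perceived risk and self-efficacy, while Section 2.1 names screening rates as the future target.

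**The case against.** The strongest reply is that this is openly a pilot and the phrase is loose grant language. Section 4.1 describes the pre-post survey as measuring impact, Section 9.1 hypothesizes no more than a change, and the only numerical criterion is for feasibility and acceptability. Conduct and data would be identical under different wording. This stands as an argument about seriousness: the defect is in the stated inference. It does not rescue the wording, since the modest hypothesis in Section 9.1 shows that a modest statement of purpose would fit the study better.

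Second, the surveys are self-completed and anonymous (Section 6.1.1). This stands in part. It should reduce social desirability, though women still answer at the end of a session with staff involved. It does nothing about repeat testing, which is the stronger threat.

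Third, a reader might infer that the protocol's scope also rules out using the pilot to size the next trial. It does not. What is reserved for later is the test of efficacy or effectiveness, and Section 6.1.1 expressly lets the pilot inform the larger trial.

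Fourth, a reader might infer that the next trial will be sized on the observed change and will therefore be underpowered. The documents do not say so. Sample size estimates could mean baseline or recruitment figures, and in Section 9.4.1 the sentence names no outcome. The risk is conditional on how the result is used.

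**Conclusion.** The point holds for the word efficacy. As written, Sections 9.3 and 9.4.1 promise a conclusion that the one-group, same-session design cannot deliver and that Sections 4.1 and 6.1.1 place outside this study. This rests on the design as described and needs no numerical assumption.

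The size of any bias cannot be obtained from the documents. The 12% to 98% range depends on assumed shifts of 0.1 to 0.5 SD, a two-sided 5% level and independent women. It shows only that a significant result would not distinguish an effective program from an inert one.

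On sizing, the supported conclusion is conditional. If the immediate change in intention were taken as the between-arm effect of a trial of screening rates, that trial may be underpowered. The plan neither commits to that use nor excludes it.

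**What to change.** In both 9.3 and 9.4.1, replace the clause "To determine program efficacy and sample size estimates for a future intervention" with wording to this effect: *to estimate preliminary pre-post change with 95% confidence intervals, without inference of efficacy, and to provide planning parameters (such as recruitment, completion and baseline proportions) for a future trial*. Add one sentence stating that the observed pre-post change will not be used as the between-arm effect size of that trial.

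The cost is wording in two sections and a less favourable stated claim. No new data, participants or procedures are needed.
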